7.3 Study Vaccination Pausing Rules

A committee consisting of the representatives of the sponsor and collaboration partners, along with the principal investigator will monitor safety profiles during the study, including the study vaccination pausing rules.

The occurrence of any of the following events will lead to a pause in further study vaccination:

- More than 15% of the participants have grade 3 or severe adverse reactions, including local reactions, systemic reactions, and vital signs.

Based on the pausing criteria, the sponsor's medical monitor or designee then decides whether a study pause is warranted.

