2.1 Study Rationale

Sinovac sIPV will be supplied to multiple countries in the near future for the polio prevention. However, data on concomitant vaccination of sIPV and other routine infant vaccines are still lacking. Thus, this study is designed to fill this gap.

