5.3 Exclusion Criteria for the Subsequent Vaccination

If any of the following 1)-3) occurs, it's forbidden to continue vaccination, but other study procedure can be continued according to the investigator's judgement; if the following 4) occurs, the it's up to the investigator to decide whether to vaccinate or not; if the following 5)-6) occurs, the vaccination could be postponed within the required time window.

- 1) Any newly confirmed or suspected autoimmune disease or immunodeficiency disorders;
- 2) Any serious adverse events related to vaccination in this study;
- 3) Severe allergic reactions after vaccination in this study;
- 4) Other reactions (e.g., severe pain, severe swelling, severe activity limitation, persistent high fever, etc.) or factors which are considered to have influence on the vaccination according to the investigator's judgement;
- 5) Various acute disease or acute exacerbation of chronic diseases by the time of vaccination;
- 6) Axillary temperature $\geq 37.3^{\circ}\text{C}$.

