7.4 Study Early Termination Rules

The occurrence of any of the following situation will lead to early termination of the study:

- After the pausing of the clinical trial, the investigator and sponsor will jointly discuss and decide whether to terminate the trial;
- The sponsor requests complete termination of the trial and explains the reason;
- The ethics committee requests complete termination of the trial and explained the reason;
- The regulatory agency requests complete termination of the trial and explained the reason.

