8.5.7 Safety Oversight

An independent DSMB will be constituted of experts from various fields of medicine who are external to sponsor's organization. The DSMB will oversee the study in terms of safety data as per DSMB charter. DSMB will have the authority to halt or terminate the study in case of any safety signals.

The independent DSMB is applicable both for Pakistan and Bangladesh.

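### The single pausing trigger in Protocol 7.3 pools co-administered and staggered infants, leaves open whether a pause must follow, and is not linked to the DSMB

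*Protocol*

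**What the plan says.** Protocol 7.3 has one bullet under its pausing events: "More than 15% of the participants have grade 3 or severe adverse reactions, including local reactions, systemic reactions, and vital signs". It gives no group, country, dose or minimum number of infants, and does not say whether the denominator is infants enrolled or infants vaccinated.

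On who acts, 7.3 sets up a committee of sponsor representatives, collaboration partners and the principal investigator, which "will monitor safety profiles during the study, including the study vaccination pausing rules". It then says that "any of the following events will lead to a pause in further study vaccination", and closes by saying that the sponsor's "medical monitor or designee then decides whether a study pause is warranted".

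Protocol 7.4 covers what follows a pause: "the investigator and sponsor will jointly discuss and decide whether to terminate the trial". Its other bullets name the sponsor, the ethics committee and the regulator. The DSMB appears in neither section. Protocol 8.5.7 sets up an independent DSMB for both countries and states that the "DSMB will have the authority to halt or terminate the study in case of any safety signals".

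Protocol 4.1 allocates 1440 infants 1:1:1:1, so 720 are co-administered (C1, C2) and 720 staggered (S1, S2).

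**The concern.** The trial exists because, in the words of Protocol 2.1, "data on concomitant vaccination of sIPV and other routine infant vaccines are still lacking". An excess of severe reactions when sIPV is given alongside the routine vaccines is therefore the harm that a pausing rule here should be built to catch. A rate taken over everyone averages that excess with the staggered infants, who never receive sIPV and routine vaccines at the same visit. The written trigger is then least sensitive to the contrast that the trial was designed to study.

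If the trigger is met, the text does not settle what happens. One sentence makes the pause automatic and the next makes it discretionary. The discretion lies with the sponsor, and the two sections that govern pausing and termination do not mention the independent board. What is at stake is further doses given to 6- to 16-week-old infants while a crossed limit is debated.

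**Working it through.** **Inputs from the documents.** Threshold above 15% (7.3); 1440 infants, 720 co-administered and 720 staggered (4.1). The 15% is set rather than derived, so there is no figure of the plan's own to reproduce.

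**Inputs assumed.** The documents give no expected grade 3 rate. I take 2% to 5% as background (the staggered rate, pS) and vary the co-administered rate, pC. Looks are after every 50 or 100 infants, with random mixed accrual and outcomes known at once.

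**Break-even.** Pooled rate = (720·pC + 720·pS)/1440 = (pC + pS)/2. This exceeds 0.15 when pC > 0.30 − pS.

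- pS = 0%: 30%
- pS = 2%: 28%
- pS = 5%: 25%
- pS = 10%: 20%

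As a count, 0.15 × 1440 = 216, so 217 infants are needed. If all were co-administered, that is 217/720 = 30.1%. The dilution is thus about two-fold at low background and shrinks as background rises.

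**Probability that the pooled rule is met.** The full-enrolment column is the exact binomial probability of more than 216 events. The repeated-looks column comes from 20,000 simulated trials per setting and spans both backgrounds and both look schedules.

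| True co-administered rate | Full enrolment, pS = 2% | Full enrolment, pS = 5% | Repeated looks |
|---|---|---|---|
| 20% | <0.01% | 0.2% | about 10% to 42% |
| 25% | 3.6% | 48.2% | about 45% to 89% |
| 30% | 86.0% | 99.6% | about 97% or more |

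The 48.2% is no surprise, since 25% is the break-even at a 5% background. Repeated looks are closer to how a pausing rule is used. They give higher figures because a small early count can cross the limit by chance.

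**Same 15% limit on co-administered infants alone.** At full enrolment this needs 109 of 720. At a true 20% the probability is above 0.999. At a single look with 100 co-administered and 100 staggered infants and a true 25%, the arm-specific limit is met with probability 0.989. The pooled limit is met with probability 0.218 (pS = 2%) or 0.451 (pS = 5%).

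**False pauses under a two-arm rule.** With at least 50 infants in an arm, the same looks and the same true rate in everyone, either arm crosses in under 1% of trials at 5%, about 7% at 8%, and about 21% to 28% at 10%.

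**Text comparison.** In 7.3 the committee only monitors, and the one named decider is the medical monitor or designee. The clash within 7.3 is therefore between a mandatory and a discretionary pause. The gap with 8.5.7 is that the body with power to halt is absent from the procedure.

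**The case against.** The trigger is not the only safeguard, and the others are substantial. The DSMB may halt or terminate on any safety signal in both countries, and nothing in 7.3 or 7.4 takes that power away. The Bangladesh annex stops enrolment after the first 50 infants until the DSMB approves; about 25 of them (50 × 2/4) would be co-administered. The trial is open-label (6.3), so an imbalance by arm can be seen. SAEs reach the sponsor within 24 hours (8.5.6). Under 5.3, an infant with "Any serious adverse events related to vaccination in this study" gets no further doses. The vaccine is licensed and WHO-prequalified, and no vaccine-related SAE was reported in its licensed trials, which vaccinated 739 infants (2.2.3), so a 25% grade 3 rate is an extreme scenario. At backgrounds of 8% to 10%, the pooled rule with repeated looks is met in about 99% or more of trials at that rate.

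All of this stands, and it lowers the risk. It does not repair the written trigger or say which sentence governs once the limit is crossed. The first-50 hold is one early look in one country, and the Pakistan annex has no equivalent.

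A reader might go further and infer that the trial lacks effective independent oversight, or that one vaccine-related death would go unreviewed because it does not reach 15%. The documents do not support either. Section 8.5.7 covers any safety signal under a DSMB charter that was not available for this review, and that charter may already provide for ad hoc review. A reader might also infer that 7.3 names rival deciders; it names one.

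**Conclusion.** The point holds as a weakness of the written rule, not as a failure of safety oversight overall. The dilution is algebra: under equal allocation the co-administered rate must exceed 30% minus the staggered rate. It rests on reading the denominator as all participants, which is the literal reading, since 7.3 states no grouping.

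The detection probabilities are illustrations that depend on assumed rates. They should be quoted with their sensitivity to the true rate and not as a fixed property of the rule. It would be tempting to say that the trial would usually miss harm from co-administration. That does not follow: at a true 30% the pooled rule is met in about 97% or more of trials with repeated looks, and at higher backgrounds dilution matters less.

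The mandatory-versus-discretionary clash and the absence of the DSMB from 7.3 and 7.4 rest on the text alone and need no assumption. Together these justify an amendment.

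**What to change.** In Protocol 7.3:

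- Define the denominator as infants vaccinated to date.
- Apply the 15% limit to reactions of grade 3 or higher, separately in co-administered (C1+C2) and staggered (S1+S2) infants, once an arm has at least 50 vaccinated infants.
- State that crossing the limit pauses vaccination pending DSMB review, in place of the medical monitor's discretion.

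In Protocol 7.4, add the DSMB to those who can end the study, to match 8.5.7. Review by country within arm can go to the DSMB without an automatic pause.

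The cost is a short text amendment and a running tabulation by arm. No new committee, visit or data item is needed: arm is already recorded, and SAP 7.1.5 already groups safety as combined C and combined S, though for final tables only. The downside is the false-pause chance shown in the working. It is small at a 5% background; if the expected background is near 10%, a minimum larger than 50 would be preferable.

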7.4 Study Early Termination Rules

The occurrence of any of the following situation will lead to early termination of the study:

- After the pausing of the clinical trial, the investigator and sponsor will jointly discuss and decide whether to terminate the trial;
- The sponsor requests complete termination of the trial and explains the reason;
- The ethics committee requests complete termination of the trial and explained the reason;
- The regulatory agency requests complete termination of the trial and explained the reason.

8. STUDY ASSESSMENTS AND PROCEDURES

Guardians of potential participants should sign an informed consent form (ICF) before performing any study specific procedures. Participants will undergo study procedures at the time points specified in the Schedule of Activities (SoA). Protocol waivers or exemptions are not allowed.

All screening evaluations must be completed and reviewed to confirm that potential participants meet all eligibility criteria. The investigators will maintain a screening log to record details of all participants screened and to confirm eligibility or record reasons for screening failure, as applicable.

Every effort should be made to ensure the protocol-required tests and procedures are completed as described. When a protocol-required test cannot be performed, the investigator will document the reason for the missed test and any corrective and preventive actions that he or she has taken to ensure that processed as possible. In addition, the study team must be informed of these incidents in a timely manner.

All needed materials for collection, handling, storage, and shipment of samples will be provided to the investigator site prior to initiation of the study.

8.1 Immunogenicity Assessments

8.1.1 Blood Collection and Laboratory Testing

Blood samples from all participants will be obtained for humoral immunogenicity testing at the visits specified in the SoA. All the serum samples for the immunogenicity assay will be sent to the assigned laboratory for analysis. In terms of antibody testing, the laboratory method and definition of immune response are summarized in the following table:

Table 5 Laboratory Testing Method and Definition of Immune Response

Antigens	Method	Category of antibody	Cutoff	Definition of immune response
Poliovirus type 1-3	Micro-neutralization	Neutralizing antibody	≥1:8**	Seroconversion: pre-vaccination titer <1:8 and post vaccination titer ≥1:8, or 4-fold titer increase in case that pre-vaccination titer ≥1:8 Sero-protection: ≥1:8
DT	ELISA	IgG	≥0.1 IU/ml**	Sero-protection: ≥0.1 IU/ml
TT	ELISA	IgG	≥0.1 IU/ml**	Sero-protection: ≥0.1 IU/ml
PT	ELISA	IgG	≥20EU/ml	Seropositivity: ≥20EU/ml
FHA	ELISA	IgG	≥20EU/ml	Seropositivity: ≥20EU/ml
PRN	ELISA	IgG	≥20EU/ml	Seropositivity: ≥20EU/ml
HepB	ELISA	IgG	10 mIU/ml**	Sero-protection: ≥10 mIU/ml
Hib	ELISA	IgG	0.15µg/mL**	Sero-protection: ≥0.15µg/mL
Pneumococcal*	ELISA	IgG	0.35µg/mL**	Sero-protection: ≥0.35µg/mL

*The following serotypes will be detected in this study: 1, 5, 6B, 14, 19F

**Cut-off accepted as indicative of protection.

8.1.2 Sample Management

Serum Separator tube (SST) should be used to collected the blood samples.

The blood samples collected on site for the purpose of antibody testing shall be sent to the local laboratory in time to handover with lab personnel. In this local lab, the serum will be separated from blood samples based on standard laboratory procedure and placed into two cyro tubes (no less than 1ml for serum tube A for testing, and tube B for backup). After separation, serum should be stored at -20°C or below until delivery to testing lab. The tube A serum will be shipped to testing lab of Sinovac Biotech Co., Ltd. to determine the antibody levels. Records should be kept for sample shipment sample handover, serum separation and sample storage. The shipment cost will be borne by the sponsor. The tube B serum shall be kept by the local lab until the official antibody testing report is issued, and then be destroyed as medical waste with the consent of the sponsor.

8.2 Safety Assessments

Planned time points for all safety assessments are provided in the SoA. Unscheduled clinical laboratory measurements may be obtained at any time during the study to assess any perceived safety issues. Any clinically relevant changes occurring during the study must be recorded on the AE section of the eCRF.

8.3 Physical Examinations

Physical examination will be performed on the vaccination day by the investigator or designated medically trained clinician. Any clinically relevant abnormalities or changes in severity observed during the review of body systems should be documented in the eCRF.

8.4 Vital Signs

Vital signs including height, weight, body temperature, heart rate and breathing rate will be measured during the physical examination.

For all participants, the immediate reactions for 30 minutes on site after the last injection in each vaccination visit will be observed on site. Upon the time of completion of the 30-minutes observation, body temperature will be measured for each participant. Guardians of participants will utilize the diary card to record solicited adverse events from the time of vaccination for 7 days post-vaccination of each dose. In this solicited period, guardians of participants are required to measure the participants' body temperature every day and recorded the daily temperature in the diary card.

From the time of the first vaccination and 28 days post-vaccination of the last dose, unsolicited adverse events and any SAEs will be required to recorded in the diary card. In the non-solicited period, for

participants with fevers, body temperature should be measured daily from the fever's onset until recovered, and the fever severity determined based on the highest temperature should be recorded in the diary card.

Body temperature is preferably measured via axillary temperature.

8.5 AEs, SAEs, and Other Safety Reporting

8.5.1 Definitions

The definitions of AEs follow the Good Clinical Practice (GCP) recommendations: E2A Guide on Clinical Safety Data Management of the International Conference on Harmonization (ICH)^[12].

Adverse Event (AE)

In this study, an AE will be defined as any untoward medical occurrence that occurs in a participant who is vaccinated and that does not necessarily have a causal relationship with the vaccine's administration. Therefore, an AE may be any unfavorable and unintended sign, symptom, or disease (including an abnormal finding in a laboratory test), temporally associated with the vaccination product, regardless of whether or not it is considered to be related to the vaccination product.

Solicited/Unsolicited adverse events

In this study, the solicited period is from Day 0 to Day 7 after each vaccination. The unsolicited period is from Day 8 to Day 28 after vaccination for co-administration group, Day 8 to Day 14 after vaccination (Day 8 to day 28 after the last dose) for staggered administration group. Solicited AEs are used to assess the reactogenicity of the study vaccine and are predefined local (at injection site) and systemic events for which the participant is specifically questioned. Unsolicited AEs refer to the unsolicited symptoms occur within the solicited period, or all symptoms occur within the non-solicitation period. Unsolicited AEs are all AEs for which the participant is not specially questioned.

Solicited local (injection site) symptoms:

Redness, swelling, rashes, induration, and pruritus

Solicited systemic symptoms (including vital signs):

Fever (axillary temperature will be measured), acute allergic reaction, diarrhea, decreased appetite, irritability, decreased activity

Serious Adverse Events (SAEs)

A SAE is an AE that results in any of the following outcomes, whether or not it is considered to be related to the study intervention.

- Death.
- Life-threatening event (i.e., means that the subject is at risk of death at the time of the onset of the adverse event, rather than an adverse event that could result in death if the condition progresses to a more serious level over time.).
- Hospitalization or prolongation of existing hospitalization, regardless of length of stay, even if it is a precautionary measure for continued observation. Hospitalization (including inpatient or outpatient hospitalization for an elective procedure) for a pre-existing condition that has not worsened unexpectedly does not constitute a serious AE.
- Persistent or significant disability or incapacity (i.e., report if the adverse event resulted in a substantial disruption of a person's ability to conduct normal life functions, i.e., the adverse event resulted in a significant, persistent, or permanent change, impairment, damage or disruption in the patient's body function/structure, physical activities and/or quality of life.).
- Congenital anomaly or birth defect.

- An important medical event (that may not cause death, be life threatening, or require hospitalization) that may, based upon appropriate medical judgment, jeopardize the volunteer and/or require medical or surgical intervention to prevent one of the outcomes listed above. Examples of such medical events include allergic reaction requiring intensive treatment in an emergency room or clinic, blood dyscrasias, or convulsions that do not result in inpatient hospitalization.

Adverse Reactions (ARs)

Any harmful or undesired reactions to humans that may be associated with the experimental vaccine that occur in the clinical trial. There is at least a reasonable probability that a causal relationship between the experimental vaccine and the adverse event cannot be ruled out as a correlation.

Serious Adverse Reaction (SAR)

An AE that is both serious and, in the opinion of the reporting investigator or sponsor, believed to be possibly, probably, or definitely due to an investigational product or any other study treatments, based on the information provided.

Suspected Unexpected Serious Adverse Reaction (SUSAR)

A SUSAR is defined as a SAR, the nature and severity of which is not consistent with the information about the medicinal product in question set out in the investigator's brochure (IB). The information about the medicinal product can be checked in the IB-chapter RSI.

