2.3 Benefit-risk assessment

2.3.1 Risks related to study participation

Based on the existing safety data of the studied sIPV, recipients of sIPV in the present study may experience pain and/or redness at injection site, fever, diarrhea, vomiting, decreased appetite etc. Overall, the studies sIPV was well tolerated, without significant safety issues identified. As with any vaccination, there is potential for an anaphylactic reaction. Additionally, there is a theoretical possibility of risks that the sponsor is currently unaware of. To facilitate the management of these potential risks, experienced medical staff in the management of anaphylactic reaction will observe patient for at least 30 minutes following vaccination to ensure that any anaphylactic reaction occurred can be managed in a timely manner.

The vaccination schedule specified in this present study for the staggered administration groups is slightly different with the exact EPI schedule, with a two-week delay for routine infant vaccines (PCV10 & DTP-HepB-Hib vaccine) or sIPV compared to the EPI schedule. However, the vaccination schedule in any group of this study met the recommendations of the package insert of study vaccines. Immune protection in early life could be accomplished by maternal antibodies transferred from mother to offspring. Maternal antibodies are very effective in protecting neonates and infants against most infectious disease, and maternal antibodies wane over a period of 6-12 months^[8-11]. The staggered administration groups will be vaccinated with sIPV or routine infant vaccines at 2 months old of the infants, thus is not considered to pose additional risk of infectious disease among the study participants.

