3. OBJECTIVES AND ENDPOINTS

The objectives and endpoints of this clinical trial are as follows:

	Objectives	Endpoints
Primary	To evaluate the non-inferiority of immune response to polio vaccination, when administered concomitantly with routine vaccines	
 Seroconversion rates of neutralizing antibody against polioviruses of three serotypes, at 28 days after three doses of vaccination
	To evaluate the safety in terms of ARs (Vaccine-related AEs)	
 Incidence of adverse reactions within 7 days after each dose of vaccination
Secondary	To evaluate non-inferiority of immune response to diphtheria and tetanus antigens, when routine vaccines are administered concomitantly with sIPV	
 Sero-protection rate of IgG antibodies against diphtheria (DT) and tetanus (TT), at 28 days after vaccination
	To evaluate non-inferiority of immune response to acellular pertussis antigens, when routine vaccines are administered concomitantly with sIPV	
 Seropositivity rate of IgG antibodies against pertussis toxin (PT), Filamentous hemagglutinin (FHA), Pertactin (PRN), at 28 days after vaccination
	To evaluate other immunogenicity against diphtheria, tetanus, acellular pertussis antigens	
 GMC/GMFR of IgG antibodies against DT, TT, PT, FHA, PRN, at 28 days after vaccination
	To evaluate other immunogenicity of sIPV, when administered concomitantly with routine vaccines	
 Sero-protection rate of neutralizing antibody against polioviruses of three serotypes, at 28 days after three doses of vaccination GMT/GMFR of neutralizing antibodies against polioviruses of three serotypes, at 28 days after three doses of vaccination
	To evaluate the immunogenicity against hepatitis B and Hib, when routine vaccines are administered concomitantly with sIPV	
 Sero-protection rate of IgG antibodies against hepatitis B and Hib, at 28 days after vaccination GMC/GMFR of IgG antibodies against hepatitis B and Hib, at 28 days after vaccination
	To evaluate the immunogenicity against pneumococcal, when routine vaccines are administered concomitantly with sIPV	
 Sero-protection rate of IgG antibodies against pneumococcal, at 28 days after vaccination GMC/GMFR of IgG antibodies against pneumococcal, at 28 days after vaccination

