5.2 Safety Endpoints

(1) Adverse Events

➤ **Solicited Adverse Events:** including solicited local (vaccination site) and systemic AEs that occur during 7 days after each vaccination. The solicited local (vaccination site) AEs: including redness, swelling, rashes, induration and pruritus. The solicited systemic AEs: including fever, acute allergic reaction, diarrhea, decreased appetite, irritability, and decreased activity.

➤ **Unsolicited Adverse Events:** including all AEs except solicited AEs during the solicitation period, and all AEs during the non-solicitation period.

(2) Serious Adverse Events

6 Analysis Sets

(1) Full Analysis Set (FAS): Following the principle of Intention to Treat (ITT), it includes all participants who are randomized, complete at least one vaccination against the antigen to be evaluated, and have the valid immunogenicity results before the first vaccination. The participants who are vaccinated erroneously will be analyzed for the immunogenicity evaluation as randomized according to the ITT principle.

(2) Per Protocol Set (PPS): It is a subset of FAS which including all the participants who are eligible for this study according to the inclusion and exclusion criteria, and then randomized, complete full vaccination as protocol specified, and have valid immunogenicity results before and after the vaccination. Participants who meet the following conditions will be excluded from PPS:

- Those who has significant protocol deviations;
- Those who are vaccinated with the wrong vaccine;
- Use of protocol prohibited vaccines or drugs;
 - Other investigational or unlicensed products (drugs or vaccines);
 - Long-term use (lasting more than 14 days) of immunosuppressive or other immunomodulatory drugs (inhaled or topical steroids are allowed);
 - Immunoglobulin and/or blood preparations;
- Newly diagnosed autoimmune disease, including human immunodeficiency virus (HIV) infection;
- Other situations affecting the evaluation of vaccine immunogenicity.

For group C1 and S1, FAS and PPS will be defined for Nab against polioviruses of serotype I, II, III, respectively. For group C2 and S2, FAS and PPS will be defined for IgG antibodies of diphtheria, tetanus, pertussis (including PT, FHA and PRN), hepatitis B, Hib and pneumococcal (including serotypes of 1, 5, 6B, 14 and 19F), respectively.

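### Injection-site pain and vomiting are the only two reactions named in Protocol 2.3.1 that are neither solicited nor given a symptom-specific grade, so they are likely to be under-ascertained in the primary 7-day endpoint.

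*Protocol*

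**What the plan says.** Section 2.3.1 of the protocol says that "recipients of sIPV in the present study may experience pain and/or redness at injection site, fever, diarrhea, vomiting, decreased appetite etc". That is six named reactions, in a list left open at the end.

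Section 8.5.1 sets the solicited local symptoms as "Redness, swelling, rashes, induration, and pruritus" and the solicited systemic symptoms as fever plus "acute allergic reaction, diarrhea, decreased appetite, irritability, decreased activity". The synopsis gives the same lists. SAP section 5.2 repeats them: local terms "including redness, swelling, rashes, induration and pruritus" and systemic terms "including fever, acute allergic reaction, diarrhea, decreased appetite, irritability, and decreased activity".

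Section 8.5.1 assigns solicited events the job of measuring reactogenicity, and defines unsolicited events as those about which the participant is not specifically asked. An off-list symptom on Days 0 to 7 is an unsolicited event.

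On grading (section 8.5.4), Table 7 has one row for redness, rash, induration and swelling and one for pruritus. Table 8 covers the six solicited systemic terms. Table 9 is a generic 1-to-5 scale for unsolicited symptoms.

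The primary safety endpoint in section 3 is "Incidence of adverse reactions within 7 days after each dose of vaccination". It is not restricted to solicited events.

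**The concern.** The protocol names six reactions, builds its solicited list around four of them, and does not say why the other two are left out. For those four, guardians are asked directly and each symptom has its own severity scale. For pain and vomiting, capture depends largely on someone raising them unprompted.

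Tolerability is in the trial's title and 7-day reactions are a primary endpoint. Local pain bears directly on the co-administration question, because the country annexes give groups C1 and C2 several vaccines at each vaccination visit.

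The comparison between arms is also exposed. The trial is open-label, and SAP sections 7.1.5 and 7.8.1 compare combined group C with combined group S. Under protocol sections 8.5.5 and 10.2 the diary is checked differently. After each dose, the co-administration groups get a telephone call at Day 14 and a face-to-face review at Day 28. The staggered groups get a face-to-face review at Day 14 after each vaccination, and at Day 28 after the last. Events that rely on being mentioned are the ones most sensitive to such differences.

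**Working it through.** **Step 1. Compare the named reactions with the lists and tables.**

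| Named in Protocol 2.3.1 | Solicited (synopsis, Protocol 8.5.1, SAP 5.2) | Symptom-specific grade |
|---|---|---|
| Injection-site redness | Yes | Table 7 |
| Fever | Yes | Table 8 |
| Diarrhea | Yes | Table 8 |
| Decreased appetite | Yes | Table 8 |
| Injection-site pain | No | None (Table 9 applies) |
| Vomiting | No | None (Table 9 applies) |

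Four of six are covered. The two gaps are the same in all three places, so this is not a slip in one list.

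**Step 2. Trace how the two symptoms reach the endpoint.** Pain or vomiting on Days 0 to 7 is recorded as an unsolicited event (8.5.1) and graded on Table 9 (8.5.4). It counts as a reaction if judged definitely, probably or possibly related (Table 6; SAP 7.1.2), and it enters the SAP 7.8.1 table of related events with onset at 0-7 days. The endpoint definition therefore includes them. What is weaker is ascertainment.

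**Step 3. Illustrate the size.** The plan states no rate for either symptom, so there is no figure to reproduce and every input here is an assumption. For one 7-day window let:

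- b = proportion with any other reaction, 20% to 40%
- q = true proportion with pain or vomiting, 5% to 20%
- c = share of those captured without solicitation, 25% to 75%

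If pain or vomiting occurs independently of the other reactions:

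- true incidence of any reaction = 1 - (1 - b)(1 - q)
- recorded incidence = 1 - (1 - b)(1 - cq)
- shortfall = (1 - b) × q × (1 - c)

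| Case | b | q | c | True | Recorded | Shortfall |
|---|---|---|---|---|---|---|
| Smallest | 40% | 5% | 75% | 43.0% | 42.25% | 0.60 × 0.05 × 0.25 = 0.75 points (about 0.8) |
| Middle | 30% | 10% | 50% | 37.0% | 33.5% | 0.70 × 0.10 × 0.50 = 3.5 points |
| Largest | 20% | 20% | 25% | 36.0% | 24.0% | 0.80 × 0.20 × 0.75 = 12 points |
| Full capture | any | any | 100% | - | - | 0 |

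If pain tends to occur in infants who also have another recorded reaction, the shortfall is smaller than shown.

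**Step 4. Illustrate unequal capture.** Give both arms b = 30% and q = 10%, so the true incidence is 37% in each. With c = 75% in one arm, recorded incidence is 1 - 0.70 × 0.925 = 35.25%. With c = 25% in the other, it is 1 - 0.70 × 0.975 = 31.75%. A gap of 3.5 points then arises from collection alone. The documents give no basis for saying which arm would be captured better.

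**The case against.** Several stronger readings are tempting, and the documents do not support them.

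- **That the two symptoms are ungraded.** Table 9 grades any unsolicited symptom from 1 to 5. Only a symptom-specific scale is missing.
- **That the endpoint will certainly undercount them.** Related unsolicited events on Days 0 to 7 are inside the endpoint, so with full spontaneous reporting nothing is lost.
- **That collection is purely passive.** Staff observe each infant for 30 minutes after vaccination, guardians fill in the diary daily, and study staff verify events at the scheduled checks. This narrows the gap but does not close it, because none of these steps prompts for pain or vomiting by name.
- **That section 5.3 depends on a solicited pain grade.** Its item begins "Other reactions (e.g., severe pain, severe swelling, severe activity limitation, persistent high fever, etc". These are examples, and the decision is left to the investigator's judgement.
- **That pain and vomiting are known to be common.** Section 2.3.1 says only that they may occur. The post-marketing summary in section 2.2.3 describes the non-serious reports as mainly fever and injection-site erythema, swelling and induration. Reaction rates from the earlier trials are referred to the Investigator's Brochure, which is not among the documents.

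The best defence of the omission is that infants this young cannot report pain, and that irritability, decreased activity and decreased appetite, all solicited, would pick up much of it. Part of this stands. Such an infant may already count as having a reaction, which reduces the shortfall in the any-reaction rate. But irritability does not identify injection-site pain, so the rate of pain itself stays poorly measured. Nor can subjectivity explain the gap, since pruritus is solicited and has its own grading row.

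It is also true that SAP section 7.6 sets no safety hypothesis and that both arms use the same list. The consequence is a less reliable descriptive rate and arm comparison. The trial's non-inferiority conclusions are not affected.

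**Conclusion.** The point holds as a limited measurement gap. Injection-site pain and vomiting are the only two of the six reactions named in section 2.3.1 that are not solicited and lack a symptom-specific grade, and neither document says why. They count in the primary 7-day endpoint as unsolicited events, but they are likely to be under-ascertained, and reporting could differ between arms.

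The size cannot be derived from the documents. The range of about 0.8 to 12 points is an illustration that depends on the assumed rates, the assumed capture shares and independence from other reactions; zero remains possible. It should not be quoted as an estimate for this trial. The change is worth making because it is cheap and concerns a primary safety endpoint. Leaving it undone would not invalidate the trial.

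**What to change.** Reconcile section 2.3.1 with the synopsis, section 8.5.1, Tables 7 and 8, and SAP section 5.2:

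1. Add observer-assessed injection-site pain or tenderness to the solicited local list and vomiting to the solicited systemic list, in the protocol, the SAP and the diary card.
2. Add a symptom-specific row for pain to Table 7 and for vomiting to Table 8. Take these from the grading guideline cited in section 8.5.4 if it contains them; its content is not in the documents, so this has to be checked.
3. If the omission was deliberate, state the reason and how the two symptoms are to be captured and graded.

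The cost is a protocol and diary amendment with brief site training. If the change is made during enrolment, infants already followed will have these symptoms only as unsolicited events, so the endpoint will mix two ascertainment methods. In that case, tabulate pain and vomiting on Days 0 to 7 by group and by collection method, and flag those collected as unsolicited. If follow-up is too far advanced for an amendment, a SAP-only step remains: tabulate both symptoms by group for Days 0 to 7, mark them as unsolicited, and state the limitation in the report.
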